### 3.2 Randomization and Blinding

Patients will be assigned treatment according to a 1:1:1 randomization schedule produced by inVentiv Health Clinical. The randomization code will not be available to the bioanalytical division of inVentiv Health Clinical until the clinical and analytical phases of the study have been completed.

Blinding of study treatments to the patient, site staff, and Sponsor will be maintained during the study using a double-dummy technique. Each patient will be dispensed with an IWRS-assigned kit, labeled with a unique kit ID at Visit 3, 4 and 5. Each kit will contain 3 bottles labeled with A, B, and C with 35 capsules each, which will be necessary to cover the period between 2 visits. The kits should be returned by the patient at the next visit and a new kit will be dispensed. Each patient should take 1 capsule from each bottle twice a day. The study will be double-blind. Patients will receive 1 of 3 different treatment kits, identical in appearance, as outlined in table below.

Treatment Group	Bottle A	Bottle B	Bottle C
IBD98-M 0.8 g/day	200 mg IBD98-M	200 mg IBD98-M	Matching Placebo
IBD98-M 1.2 g/day	200 mg IBD98-M	200 mg IBD98-M	200 mg IBD98-M
Placebo	Matching Placebo	Matching Placebo	Matching Placebo

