### 3. STUDY DESIGN AND PLAN

Study IBD98-M-2002 is a Phase 2a, multicenter, randomized, double-blind, parallel group, placebo-controlled trial in patients with active, mild to moderate UC. It is being conducted as an exploratory proof-of-concept study to investigate the clinical efficacy of IBD98-M delayed-release capsules (in a fixed combination) over a 6-week treatment period and a 2-week follow-up period.

Patients will be screened for study enrollment up to 2 weeks prior to randomization (Visit 3). During the screening period, patients will be evaluated with laboratory tests, physical examinations, and sigmoidoscopy. To be eligible, patients are to have a score of  $\geq 4$  and  $\leq 10$  on the modified UCDAI, and a score of  $> 1$  on the endoscopy subscore would be included. In addition, the diagnosis of UC must be confirmed visually by endoscopy images and also by histologic evidence in the past. After the screening visits, eligible patients will be randomized to 1 of 3 study groups:

- (1) IBD98-M 0.8 g/day (mesalamine 0.8 g with sodium hyaluronate 92 mg),
- (2) IBD98 M 1.2 g/day (mesalamine 1.2 g with sodium hyaluronate 138 mg), or
- (3) Placebo.

Up to 51 patients will be enrolled in this study (including drop-out patients), with 17 patients randomized to each treatment group. Study blind will be maintained using a double-dummy technique.

Eligible patients will be randomized centrally via an Interactive Web Response System (IWRS), and each patient will receive 3 capsules twice a day (BID) for a period of 6 weeks, administered orally in 1 of the following regimens:

- Patients in the 0.8 g/day group will receive 2 capsules of IBD98-M (200 mg of mesalamine/23 mg of sodium hyaluronate) and 1 placebo capsule BID.
- Patients in the 1.2 g/day group will receive 3 capsules of IBD98-M (200 mg of mesalamine/23 mg of sodium hyaluronate) BID.
- Patients in the placebo group will receive 3 placebo capsules BID.

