### **3.1 Study Treatments and Assessments**

IBD98-M (mesalamine, United States Pharmacopeia [USP]; and sodium hyaluronate) drug product is a delayed-release capsule. Each capsule is filled with multiple-layer pellets containing 200 mg of mesalamine and 23 mg of sodium hyaluronate. Each pellet consists of a microcrystalline cellulose inner core, which is coated first with mesalamine, USP; then with sodium hyaluronate, and finished with an enteric coating film.

The enteric-coated pellets are designed to allow the release of mesalamine and sodium hyaluronate from the pellets at or above pH 6.8 at the terminal ileum (ascending colon).

The matching placebo capsule will be indistinguishable from the drug capsule. The capsules (placebo or drug) are packaged, 35 count per bottle, into 60-cc white, wide-mouth, round HDPE (High Density Polyethylene) bottles sealed with an aluminum foil pad and covered with a polypropylene plastic cap. The product stability is for 24 months when the product is stored in a stability chamber of 25° C +/- 2° C. The product should be stored at 15° to 25° C [59° to 77° F].

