- e. Modified UCDAI on Days 0 and 42 should be complete modified UCDAI score including the endoscopy subscore. Modified UCDAI at Screening Visit 2, Visit 4, and Visit 5 should be partial modified UCDAI score including only stool frequency, rectal bleeding and physician's global assessment.
- f. Screening sigmoidoscopy must be performed on Day -7 to Day -1.
- g. No distribution of diary at Visit 6. Only check diary from Visit 5
- h. A sample will be collected and cultured during screening and at any point in the study when a patient becomes symptomatic, including worsening or return of disease activity.
- i. To be performed prior to dosing.
- j. Treatment distribution will be done at Visits 3, 4, and 5. Treatment accountability will be done at Visits 4, 5, and 6. All unused medication is to be returned at Visits 4, 5, and 6.

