### 7.2 Protocol Deviations

Protocol deviations are deviations that occurred before or during the randomized treatment period. Protocol deviations will be recorded from the screening visit. The following criteria are considered as major protocol deviations:

- Patient did not satisfy all inclusion/exclusion criteria.
- Patient was unblinded to the study treatment or if treatment code is broken by site without medical emergencies of patient.
- Treatment compliance is not in the range of 80% to 120%.
- Patient took concomitant medication during the study which was forbidden in the protocol.
- Patient is treated with any other study medication in another clinical study.

- Missing primary efficacy data at baseline and the end of treatment visit.

Protocol deviations will be identified at the study site and recorded in an Excel spreadsheet by a sponsor representative and shared with the inVentiv Health Clinical statistical programming team before database lock.

The number and percentage of ITT patients experiencing at least one major protocol deviation and the number and percentage of ITT patients with each type of major protocol deviation will be summarized by treatment group and overall.

All protocol deviations will be listed.

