### **7.7 Study Drug Exposure and Compliance**

Duration of exposure, in days, will be calculated for each patient as the date of the last dose of study medication minus the date of the first dose of study medication, plus 1 day. Duration of exposure will be summarized descriptively by treatment group and overall for the safety population.

In general, percent dosing compliance for an individual patient will be computed as:

$$(\text{number of capsules taken}) / (\text{number of capsules expected to be taken}) \times 100\%$$

Percent dosing compliance between two visits will be computed where:

$$\text{number of capsules taken} =$$

- number of capsules dispensed at the earlier visit
- number of capsules returned (from those dispensed at the earlier visit)
- number of capsules reported lost/damaged (of those dispensed at the earlier visit)

and

$$\text{number of capsules expected to be taken} =$$

$$(\text{date of the later visit} - \text{date of the earlier visit} [+1 \text{ if the earlier visit is Visit 3}]) \times 6$$

Percent dosing compliance for the whole study will be computed where:

$$\text{number of capsules taken} =$$

- number of capsules dispensed at all visits
- number of capsules returned at all visits
- number of capsules reported lost/damaged at all visits

and

$$\text{number of capsules expected to be taken} =$$

$$(\text{date of the last visit} - \text{date of the first dose} + 1) \times 6$$

Percent dosing compliance will be summarized descriptively at Visits 4, 5, and 6, and for the study as a whole, by treatment group and overall for the safety population. Dosing noncompliance is defined as taking less than 80% of study medication capsules during the whole treatment period. Overall dosing compliance and by visit dosing compliance will be categorized as <80%, 80% to 100%, and >100%, and summarized descriptively by treatment group and overall for the safety population.

All study drug administration, accountability, and compliance data will be listed.

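### The 35-capsule bottles last 17.5 days, but the visit windows allow gaps of up to 20 days with all leftovers returned, so a fully adherent patient can run out before the next visit

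*SAP*

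**What the plan says.** SAP 3 sets the regimen: "each patient will receive 3 capsules twice a day (BID) for a period of 6 weeks". SAP 3.1 states that capsules "are packaged, 35 count per bottle". Under SAP 3.2 a kit has three bottles (A, B and C) "with 35 capsules each, which will be necessary to cover the period between 2 visits", and the patient takes one capsule from each bottle twice daily. On exchange, the same section says: "The kits should be returned by the patient at the next visit and a new kit will be dispensed".

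SAP Table 1 places Visits 3, 4, 5 and 6 at Days 0, 14, 28 and 42, each ± 3 days. Its footnote j has drug dispensed at Visits 3, 4 and 5 and adds: "All unused medication is to be returned at Visits 4, 5, and 6".

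SAP 7.7 computes compliance between two visits as capsules taken divided by capsules expected. Expected capsules are six per calendar day between the visits, with one day added "if the earlier visit is Visit 3".

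**The concern.** The kit is described as covering the time between two visits, yet the SAP's own windows permit intervals that it does not cover. The 35-count bottle allows for a late second visit but not for an early first one. Table 1 permits both together.

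There are two consequences.

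- **Dosing.** Between Visits 4 and 5, the shortfall interrupts treatment inside the 6-week course. Between Visits 5 and 6, it falls after Day 42 (with Visit 3 on Day 0) but before a late Visit 6, so a patient may be off drug just before the primary assessment. The SAP does not say whether dosing continues after Day 42, although the compliance formula expects capsules up to the visit.
- **Compliance.** A patient who took every capsule supplied scores below 100% for the interval. In the summaries this cannot be told apart from missed doses.

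**Working it through.** **Inputs (all SAP).** 35 capsules per bottle and three bottles per kit, so 105 per kit (3.1, 3.2). Use is 2 capsules per bottle per day, or 6 per kit per day (3.2). Visits fall on Days 0, 14, 28 and 42, each ± 3 (Table 1). All unused drug is returned at Visits 4, 5 and 6 (Table 1, footnote j).

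**Where 35 is enough.** The nominal gap of 14 days needs 14 × 2 = 28 per bottle. An on-time visit followed by one 3 days late is 17 days and needs 34. Both are covered.

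**Where it is not.** Days covered: 35 / 2 = 17.5. Longest in-window gap: 14 + 3 + 3 = 20 days, needing 20 × 2 = 40 per bottle. That is 5 capsules short, or 2.5 days.

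**Effect of clock times.** Depending on whether each visit comes before or after that day's doses, a gap of L days needs 2L − 1, 2L or 2L + 1 capsules per bottle. Interval compliance for a patient who takes all 105 capsules is 105 / (6L).

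| Gap (days) | Need per bottle | Days short | Compliance |
|---|---|---|---|
| 17 | 33 / 34 / 35 | 0 / 0 / 0 | not supply-limited |
| 18 | 35 / 36 / 37 | 0 / 0.5 / 1 | 105/108 = 97.2% |
| 19 | 37 / 38 / 39 | 1 / 1.5 / 2 | 105/114 = 92.1% |
| 20 | 39 / 40 / 41 | 2 / 2.5 / 3 | 105/120 = 87.5% |

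The same percentages are adherence thresholds: a patient runs out only if adherence in that interval is above them.

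**Permitted schedules.** Each pair of visits has 7 × 7 = 49 in-window day pairs.

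| Gap (days) | Visits 4-5 (day supply ends) | Visits 5-6 (day supply ends) |
|---|---|---|
| 18 | 11-29 (28.5), 12-30 (29.5), 13-31 (30.5) | 25-43 (42.5), 26-44 (43.5), 27-45 (44.5) |
| 19 | 11-30 (28.5), 12-31 (29.5) | 25-44 (42.5), 26-45 (43.5) |
| 20 | 11-31 (28.5) | 25-45 (42.5) |

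That is 3 + 2 + 1 = 6 of 49 for each interval. It counts permitted schedules and is not an expected frequency.

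**Can both intervals run short?** Each needs the later visit's offset from target to exceed the earlier one's by at least 4 days. Both together need Visits 4 and 6 to differ by at least 8 offset days, and the windows allow only 6. So 0 of 7 × 7 × 7 = 343 combinations run short twice.

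**Loss inside the course.** With Visit 3 on Day 0, the first interval is at most 17 days and is covered. The Visit 5 kit never ends before 25 + 17.5 = Day 42.5. Only Visits 4-5 can therefore cost treatment inside the 42 days: 2.5/42 = 6.0%, or 3/42 = 7.1% at the least favourable clock times.

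**First kit under SAP 7.7.** The added day makes the expected count (16 + 1) × 2 = 34 per bottle at 16 days, (17 + 1) × 2 = 36 at 17 days, and (20 + 1) × 2 = 42 at 20 days, which is possible only if Visit 3 is 3 days early. In that last case interval compliance would be 105/126 = 83.3%.

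**Source of the shortage.** Three kits hold 315 capsules. The longest permitted treatment period, Day −3 to Day 45, has an expected count of (48 + 1) × 6 = 294. Total supply is enough; returning leftovers at each visit creates the gap.

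**The case against.** SAP 3.2 presents no calculation. It describes a kit for a nominal 14-day interval, and 35 against 28 is a 25% margin. On that reading this is a remark about supply margin and not a wrong figure. That is fair as to kind, but the stated purpose is still not met across the schedule the SAP permits.

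Resupply and visit-spacing rules normally sit in the governing protocol. The SAP is based on Protocol Amendment 3. The protocol available here is a different version, with one 6-week kit (Protocol 8.4), so the absence of a cap or reserve supply from these documents is weak evidence that none exists. This stands and limits confidence.

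The Visit 5-6 shortfalls come after six weeks of drug have been supplied (Visit 3 on Day 0), and a compliance denominator is not a dosing instruction. This also stands for the prescribed course. What remains there is a possible drug-free period before a late Visit 6 and a compliance figure that misleads.

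Finally, no planned result changes category. The interval values stay within the 80% to 120% range of SAP 7.2 and in the 80% to 100% band of SAP 7.7. SAP 7.7 also promises that "All study drug administration, accountability, and compliance data will be listed", so a long interval with nothing returned could be found by hand. All of this is correct, and it is why the point is minor.

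**Conclusion.** The concern holds, at low severity. If the SAP is followed exactly, a fully adherent patient can be without drug for about 2.5 days between dispensing visits. Inside the 6-week course this arises only between Visits 4 and 5 (with Visit 3 on Day 0), in 6 of 49 permitted day pairs, and it costs at most 6.0% of treatment days, or 7.1% at the worst clock times. Three of those six pairs are 18-day gaps, where the shortfall is between nothing and one day.

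This assumes the SAP scheme as written: one kit per interval, full return of leftovers, no reserve supply and no cap on spacing. Whether Amendment 3 adds a cap or extra supply is unknown, as is how often early-then-late visits occur and what effect a short interruption has on remission. The primary ITT analysis is unchanged.

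**What to change.** First confirm whether Protocol Amendment 3 already limits visit spacing or provides extra supply.

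- **Preferred.** State in the governing protocol's visit schedule, and repeat in SAP Table 1, that the visit after each dispensing visit must be no more than 17 days later. This always leaves an in-window day: Visit 4 on Day 11 allows Visit 5 up to Day 28, and Visit 5 on Day 25 allows Visit 6 up to Day 42. A 17-day gap needs 33 to 35 capsules per bottle, so 35 is enough at any clock times. For the first kit use 16 days if an adherent patient should read 100% under the SAP 7.7 formula. The cost is one sentence and slightly less scheduling flexibility.
- **Alternative, only before packaging.** Supply at least 40 capsules per bottle. Supplying 42 covers the worst clock times (41) and the first kit under the added-day rule with Visit 3 three days early (42). The cost is a change to the 35-count packaging.
- **If dispensing is complete.** Flag intervals longer than 17.5 days in the compliance listing, so that supply-limited dosing is not read as non-adherence. The cost is one flag in a listing that is already planned.

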### 3.3 Sample Size Justification

Simon's randomized Phase 2 design was used. The average remission rate of placebo is approximately 0.2. With power of 0.8, and the difference in remission rates between the best treatment and the other treatments  $\geq 0.18$ , each arm requires 17 patients, giving the total number of patients to be enrolled as 51. This enrollment is adequate as it will provide 28.2% precision with a 95% confidence interval for evaluation of the difference between study treatment and placebo (i.e., the primary objective), where precision is defined as 1/2 width of the confidence interval. Based on this rationale, 51 patients will be enrolled, with 17 patients randomized to each group.

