## 1. INTRODUCTION

The purpose of this document is to provide details about the statistical analysis methods specified in the study protocol IBD98-M-2002: A Phase 2a, Multicenter, Randomized, Double-blind, Parallel-group, Placebo-controlled Trial of IBD98-M Delayed-release Capsules to Induce Remission in Patients with Active, Mild to Moderate Ulcerative Colitis, sponsored by Holy Stone Healthcare Co., Ltd. This Statistical Analysis Plan (SAP) is based on the Protocol Amendment 3 dated 09 May 2017.

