## 2. STUDY OBJECTIVES

### Primary

To compare the percentage of patients in ulcerative colitis (UC) remission at Week 6 for each of the two IBD98-M dose groups versus placebo (remission defined as the modified Ulcerative Colitis Disease Activity Index [UCDAI] score of  $\leq 1$ , with a score of 0 for rectal bleeding and stool frequency, no mucosal friability, and sigmoidoscopy score not exceeding 1).

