## 6. STATISTICAL CONSIDERATIONS

For efficacy and safety data, descriptive statistics (n, mean, standard deviation [SD], median, minimum, and maximum for continuous data, and n [%] for categorical data) will be presented. Similarly, wherever applicable, changes from baseline will be summarized in the same manner.

Unless otherwise stated, the denominator for percentages will be based on the number of patients in each treatment group who provided non-missing responses to the categorical variable, all statistical tests will be two-sided and at the 5% level of significance, and all differences between treatment groups will be presented with two-sided 95% confidence intervals (CIs). All p-values will be displayed to three decimals and rounded using standard scientific notation (e.g., 0.XXX). If a p-value less than 0.001 occurs it will be shown in tables as <0.001. If a p value greater than 0.999 occurs it will be shown in the tables as >0.999.

Unless otherwise stated, percentages will be presented to one decimal place in all summaries.

Minimum and maximum values will be presented to the same number of decimal places as collected on the case report form (CRF) or within the laboratory panel; mean and median will be presented to one decimal place more than CRF data; standard deviation will be presented to two decimal places more than CRF data.

Dates will be presented in format DDMMYY and numbering for tables, figures, and listings will follow ICH E3.

All statistical analyses will be performed using Statistical Analysis System (SAS®) version 9.4 or higher (SAS Institute, Cary, NC).

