### 7.8.1 Primary Efficacy Endpoint

The primary efficacy endpoint is the percentage of patients in remission at Week 6. A patient is considered to be in remission (a responder) at Week 6 if the patient has a modified UCDAI score of  $\leq 1$ , with a score of 0 for rectal bleeding and stool frequency, no mucosal friability (a mucosal appearance score of  $\leq 1$ ), and sigmoidoscopy (mucosal appearance) score not exceeding 1. A patient is considered to be a non-responder if no diary data is available within the period from Day 36 to study end or endoscopy within the period from Day 28 to study end (a non-responder imputation approach).

The number and percentage of patients who are in remission at Week 6 will be presented by treatment group, along with 95% confidence intervals constructed using the Clopper-Pearson method.

The percentage of patients in remission at Week 6 will be compared between each of the IBD98-M groups and placebo using Fisher's exact test. Each test will be 2-sided and declared statistically significant at the 0.05 level. No adjustment will be made for the two comparisons.

A bar chart of the percentage of patients in remission at Week 6 for each of the two IBD98-M groups and placebo will be presented.

As a supportive analysis, the primary efficacy endpoint will also be analyzed using the per protocol population.

Also, a sensitivity analysis will be used to assess the effects of missing data. The primary efficacy endpoint will be analyzed on the ITT population without making use of the non-responder imputation approach. Similar statistical methods will be used for the sensitivity analysis as is to be used for the primary efficacy analysis on the ITT population (which will use a non-responder imputation).

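### The 0.8 that SAP 3.3 calls power is a selection probability; each planned Fisher test has about 12% power at the 0.18 design difference

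*SAP*

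**What the plan says.** SAP 3.3 names Simon's randomized Phase 2 design, takes a placebo remission rate of about 0.2, and continues: "With power of 0.8, and the difference in remission rates between the best treatment and the other treatments" at or above 0.18, 17 patients per arm are needed, 51 in all. It then adds a second rationale, "This enrollment is adequate as it will provide 28.2% precision with a 95% confidence interval" for the difference from placebo, with precision defined as half the interval width. The section states neither the remission rates nor the interval method used for that figure.

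The supplied protocol gives the same sample size argument in the synopsis, 6.2 and 12.1, and there also attaches a type I error of 0.05. SAP 3.3 does not repeat the type I error.

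The primary objective in SAP 2 is to compare "remission at Week 6 for each of the two IBD98-M dose groups versus placebo". SAP 7.8.1 does this with Fisher's exact test, one test per dose: "Each test will be 2-sided and declared statistically significant at the 0.05 level", with no adjustment for the two comparisons. Single-group remission rates are given "along with 95% confidence intervals constructed using the Clopper-Pearson method". SAP 6 promises that "all differences between treatment groups will be presented with two-sided 95% confidence intervals (CIs", but no method is named for the interval of a difference in proportions.

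**The concern.** A selection design and a hypothesis test answer different questions. A selection design picks the arm with the highest observed rate, and its operating characteristic is the chance that this is the truly best arm. It has no significance threshold and does not control the type I error. If all three true rates are equal, one of the two active arms still ranks first two times in three. The planned analysis is a pair of significance tests, and their power is stated nowhere.

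A reader who sees power of 0.8 beside a 0.05-level primary test will assume a 20% chance of missing the design difference. If the true miss rate is far higher, a non-significant result would be read as evidence against the drug when the trial could say little either way.

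**Working it through.** **Inputs.** Three arms of 17, placebo rate 0.20 and minimum difference 0.18, all from SAP 3.3. The best arm is therefore at 0.20 + 0.18 = 0.38. Primary test: two-sided Fisher exact at 0.05, 17 against 17 (SAP 7.8.1).

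**Step 1: reproduce the plan's figure.** Let b(x) be the binomial probability of x remissions among n patients at rate 0.38. Let g(x) and G(x) be the binomial probability and cumulative probability at rate 0.20. With ties split at random among the tied arms,

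P(best arm selected) = Σₓ b(x) · [ G(x−1)² + 2·g(x)·G(x−1)/2 + g(x)²/3 ].

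| n per arm | Strictly first | Ties split at random | First or tied |
|---|---|---|---|
| 16 | 0.733 | 0.790 | 0.850 |
| 17 | 0.747 | **0.800** | 0.858 |

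Seventeen is the smallest n that reaches 0.80 with ties split. This identifies the 0.8 as a probability of correct selection. A conventional two-sided 0.05 comparison of 0.20 with 0.38 at 80% power would need 99 per arm by the usual normal-approximation formula.

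**Step 2: power of the planned test.** Sum, over all pairs (i remissions on placebo, j on active), the product of the two binomial probabilities wherever the two-sided Fisher p-value is at most 0.05:

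Power = Σᵢ Σⱼ Bin(i; 17, 0.20) · Bin(j; 17, p₁) · 1[p(i, j) ≤ 0.05].

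| True active rate p₁ | Power against 0.20 | Chance of missing it |
|---|---|---|
| 0.38 (design minimum) | 0.117 | 0.883 |
| 0.50 | 0.319 | 0.681 |
| 0.60 | 0.561 | 0.439 |
| 0.71 | 0.811 | 0.189 |

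Only the first row is a design assumption; the others show how power rises. If the difference stays at 0.18 and the placebo rate is varied from 0.10 to 0.30, power stays between 11.1% and 15.3%. At 0.38 against 0.20, about 110 patients per arm would be needed for 80% Fisher power (0.806 at 110).

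The chance that at least one dose is significantly better than placebo is 12.0% if one dose is at 0.38 and the other at 0.20, and 18.9% if both are at 0.38.

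In counts: with 3/17 remissions on placebo, 9/17 on active gives p = 0.071 and 10/17 gives p = 0.032. Significance then needs an observed difference of 7/17, or 41 points.

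**Step 3: the 28.2-point half-width.** By Wald at the design rates,

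1.96 · √[(0.38·0.62 + 0.20·0.80)/17] = 1.96 · √(0.3956/17) = 0.299.

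The Newcombe interval at the same rates runs from −0.121 to 0.443, a half-width of (0.443 + 0.121)/2 = 0.282. Wald also gives 0.282 at 0.26 against 0.20: 1.96 · √[(0.1924 + 0.1600)/17] = 0.282. At least two combinations of rates and method therefore fit, and the SAP does not say which was used. At attainable counts near the design rates (6/17 or 7/17 against 3/17), the half-width is 27.8 to 28.0 points by Newcombe and 29.1 to 29.6 by Wald.

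**The case against.** The strongest reply is that nothing has been miscalculated. SAP 3.3 names the selection design, ties the 0.8 to the best arm against the others, and arrives at the right n for that design. The study is described as exploratory proof of concept, and no decision is made to depend on Fisher significance. The SAP drops the protocol's type I error statement, and protocol section 12 lets the SAP prevail on analysis. It is the precision figure, not the 0.8, that SAP 3.3 calls adequate. The 0.18 was never set as a precision goal.

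Much of this is fair. Seventeen per arm is correct for selection, and this is a mislabel together with a mismatch between design and analysis, not a wrong sum. The exploratory setting lowers the stakes. The type I error point applies only to the protocol text. Comparing the half-width with 18 points is a yardstick brought by the reviewer, though a useful one, because an interval that wide centred near an 18-point difference includes zero.

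The main point survives. Naming the design does not turn a selection probability into power, and an exploratory label does not remove tests that are declared significant at 0.05. Nor does the precision figure tell the reader what power those tests have.

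**Conclusion.** The concern holds. The 0.8 in SAP 3.3 is the probability of correct selection (0.800 at 17 per arm with ties split at random), while the primary test has a power of 0.117 at 0.38 against 0.20, about one seventh of the stated figure. The result rests on the SAP's own placebo rate and difference, 17 evaluable patients per arm (non-responder imputation applies to the ITT population), and exact enumeration. The 12% applies to a dose whose true rate is 0.38; a dose truly at 0.20 would be declared different in 1.9% of trials.

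That 28.2 points came from a Newcombe interval at the design rates is an inference. What is certain is that its basis is not stated. This is a secondary point, and the main conclusion does not depend on it.

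**What to change.** In SAP 3.3, replace the sentence that claims power of 0.8 with:

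> With 17 patients per arm, the probability that the truly best arm has the highest observed remission rate is about 80% (ties split at random) if its true rate is 0.38 and the other two are 0.20. This is a selection probability. It is not the power of the primary test and does not control the type I error. For a dose with a true rate of 0.38 against 0.20 on placebo, each two-sided Fisher exact test at 0.05 has about 12% power. For illustration, power is 32% at 0.50 and 56% at 0.60.

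Replace the adequacy statement with the following, keeping only the figure for the method chosen:

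> Taking 0.38 and 0.20 as the observed rates, the 95% confidence interval for the difference has a half-width of [28.2 points, Newcombe / 29.9 points, Wald], which is wider than the 18-point design difference.

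Name the same interval method in SAP 7.8.1. The closing sentence of 3.3, on 51 patients with 17 per group, can stay.

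The SAP "is based on the Protocol Amendment 3 dated 09 May 2017", and the supplied protocol may be an earlier version. If the current amendment still carries the power and type I error wording in the synopsis, 6.2 and 12.1, correct it there too.

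The cost is a few sentences and a less favourable stated figure. The sample size, populations, data collection and Fisher comparisons are unchanged.
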